Study Design	
This prospective cross-sectional study (Assessment of Somatic Symptom in Chinese Community-Dwelling People, ClinicalTrials.gov identifier NCT04815863, registered on 06/12/2020) is a multicenter registry conducted in Shanghai, China, under the supervision of the Shanghai Association of Chinese Integrative Medicine.
 
A multistage and stratified systematic sampling technique will be used to choose representative districts from sixteen districts in Shanghai, which are then divided into low, medium, and high economic levels according to the per capita gross domestic product of each district in 2018. Eleven districts will be selected proportionally and randomly and represented by 105 community health service institutions. The study was approved by institutional review committees at each center. The study is compliant with the 1975 Declaration of Helsinki guidelines.
 
(1) assessment of somatic symptom disorder (SSD)
 
The Somatic Symptom questionnaire is self-administered with an abbreviated 20-item measure. Briefly, it is composed of four dimensions: physical disorders, depressive disorders, anxiety disorders and depressive and anxiety disorders. Half of the items ask about physical complaints (one item per body system). SSS-CN scores ranging from 20 to 29, 30–39, 40–59 and ≥ 60 correspond to normal, mild, moderate and severe SSD, respectively.
 
(2) assessment of depressive and anxiety disorders
 
All participants will be assessed for depressive and anxiety disorders according to the PHQ-9 and GAD-7, which evaluate the frequencies at which certain symptoms had been experienced over the last two weeks, ranging from 0 ('not at all') to 3 ('nearly every day'). The cutoff values are listed below. For PHQ-9, scores of 5–9 indicate mild depressive disorder, 10–14 indicate moderate depressive disorder, 15–19 indicate moderately severe depressive disorder and ≥ 20 indicate severe depressive disorder. For GAD-7, scores range from 0 to 21, with scores of 5–9, 10–14, and ≥ 15

	
representing mild, moderate, and severe anxiety symptom levels, respectively.
 
(3) sociodemographic and clinical characteristics
 
Sociodemographic data, including age, gender, level of education and marital status, will also be collected. A semi-structured questionnaire concerning clinical characteristics will be administered to survey participants' medical and medication histories.

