Number of Subjects	
Enrollment: 9110 [anticipate]
 
Elderly group: 6874 [anticipate]
 
Non-elderly group: 2236 [anticipate]

Enrollment Criteria	
Inclusion criteria were:
 
(1) voluntary participation and provision of written consent to participate in the study's evaluation and assessment;
 
(2) completion of the SSS-CN questionnaire, Patient Health Questionnaire-9 (PHQ-9) and Generalized Anxiety Disorder-7 (GAD- 7) questionnaires.
 
Exclusion criteria were :
 
(1) patients lacking self-assessed abilities or who refused to participate;
 
(2) patients who have been previously confirmed to have serious mental disorders, mental retardation, or dementia;
 
(3) patients with cancer or central nervous system diseases;
 
(4) patients with any missing data within questionnaire items or with more than one item missing from sociodemographic information;
 
(5) patients with any medical conditions that in the opinion of the investigators will not be appropriate to participate in the study.

Safety Assessment	Adverse events were not required in this study protocol.
Endpoints	
1. Number of Participants With Somatic Symptoms Disorder
 
2. Number of Participants With Somatic Symptoms Disorder Accompanied With Anxiety
 
3. Number of Participants With Somatic Symptoms Disorder Accompanied With Depression

Statistical Analysis	
Descriptive statistics for each group, such as counts and percentages (%) for non-continuous variables, will be reported for all sociodemographic and clinical characteristics. The prevalences of SSD of various severities for different genders and for participants diagnosed with depressive and anxiety disorders will be calculated. In order to assess whether SSD, depressive and anxiety disorders are associated with aged groups and whether depressive and anxiety disorders are associated with the severity of SSD, binary logistic regressions will be performed, adjusting for gender, educational level (middle school and below, high school, college, master and above), marital status (never married, married, divorced, widowed), hypertension (yes/no), diabetes mellitus (yes/ no), CV disease

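### About half of the SSS-CN items appear to be depressive or anxiety items, so the planned association of SSD severity with PHQ-9 and GAD-7 disorders is partly built in

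*Combined protocol and SAP*

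**What the plan says.** All references are to the Synopsis.

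- **Study Design, part 1.** The SSS-CN has 20 items. On content, "it is composed of four dimensions: physical disorders, depressive disorders, anxiety disorders and depressive and anxiety disorders". On the split, "Half of the items ask about physical complaints (one item per body system".
- **Same part, scoring.** Normal is defined by "SSS-CN scores ranging from 20 to 29"; mild SSD is 30–39, moderate 40–59 and severe 60 or more. Only the total counts, and no minimum is set for the physical items.
- **Study Design, part 2.** Depressive and anxiety disorders are classified by PHQ-9 and GAD-7.
- **Statistical Analysis.** To assess "whether depressive and anxiety disorders are associated with the severity of SSD, binary logistic regressions will be performed". The section does not say which side is the dependent variable. It also plans a table: "The prevalences of SSD of various severities for different genders and for participants diagnosed with depressive and anxiety disorders will be calculated".
- **Covariates.** Gender, education, marital status, disease indicators, surgery and antipsychotic intake. None bears on item content.
- **Endpoints 2 and 3.** "Number of Participants With Somatic Symptoms Disorder Accompanied With Anxiety" and "Number of Participants With Somatic Symptoms Disorder Accompanied With Depression".

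No analysis of the physical items alone is described, and the presence of mood content on both sides of the association is not noted as a limitation.

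**The concern.** A person with depressive or anxious symptoms should score higher on PHQ-9 or GAD-7 and also on the depressive and anxiety dimensions of the SSS-CN. That raises the SSS-CN total, and so the SSD grade, whether or not the person has any physical complaint. The planned regression cannot separate two explanations for a positive result: physical symptoms accompany mood disorder, or the two instruments partly measure the same thing.

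What is at stake is interpretation. The severity association, and any reading of endpoints 2 and 3 as physical symptoms occurring together with mood disorder, could be credited to comorbidity when some of it comes from how SSD is scored.

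**Working it through.** The plan gives no expected association, effect size or power for this analysis, so there is no figure of its own to reproduce.

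**1. Item split (from Study Design, part 1).** Half of 20 is 10 physical items; 20 − 10 = 10 others. The only other named dimensions are depressive, anxiety, and both combined. Without an item list, neither the count of mood items nor any shared wording with PHQ-9 or GAD-7 can be confirmed.

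**2. What the bands allow.** Assume an unweighted sum of items with equal ranges.
- Item minimum: 20/20 = 1.
- All physical items at minimum and the other ten at 2: 10×1 + 10×2 = 30, which is mild SSD.
- The severe band is reachable only if the item maximum is at least 60/20 = 3. Then 10×1 + 10×3 = 40, which is moderate SSD.

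Both grades can therefore be reached with no physical complaint. These are boundary cases, not typical patients.

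**3. Simplest model (all inputs assumed).** Let the total be T = (M + P)/√2, with mood half M and physical half P independent and of equal variance. Let the PHQ-9 or GAD-7 score correlate r with M only, with 20% positive. Then corr(T, PHQ/GAD) = r/√2. With SSD prevalence of 20–50%:

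| r | r/√2 | Odds ratio, SSD by total | Odds ratio, physical half only |
|---|---|---|---|
| 0.3 | 0.21 | 1.8–1.9 | 1.0 |
| 0.5 | 0.35 | 2.8–2.9 | 1.0 |
| 0.7 | 0.49 | 4.5–4.7 | 1.0 |

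**4. Item-level model (all inputs assumed).** This was a univariate logistic regression of PHQ-9 ≥5 (22% positive) on the standardised score, with N = 100,000 per setting and SSS-CN items scored 1–4. The 270 settings were 3 item-frequency patterns × physical loading 0.5 or 0.7 × mood loading 0.3, 0.5 or 0.7 × trait correlation ρ = 0, 0.3, 0.5, 0.7 or 0.85 × 0, 3 or 4 PHQ-9 items reflecting the physical trait.

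| Setting | Odds ratio per SD, total | Odds ratio per SD, 10-item physical subscore |
|---|---|---|
| ρ = 0, no physical PHQ-9 items | 1.5–4.2 | 1.0 |
| ρ = 0, 3–4 physical PHQ-9 items | 2.4–5.1 | 1.6–2.2 |
| ρ = 0.7 | 3.3–8.0 | 2.3–4.6 |

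The total/subscore ratio was 1.21–4.24 with no physical PHQ-9 items, 1.14–2.94 with three and 1.09–2.35 with four. If only five SSS-CN items were mood items, it was 1.15–1.87. Other assumed settings reached 5.2, so the upper end depends on the grid. Among simulated SSD cases, 2–28% had a physical subscore of 12 or less (minimum 10); among those with SSD plus depression, 1–46%.

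**5. How much is scale length?** With no mood items at all, comparing 20 physical items with 10 of them already gave ratios of 1.02–1.44 in one set of runs and 1.00–1.50 in another. The low ends in step 4 could therefore be length alone.

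**6. Does the direction always hold?** No. Against a hypothetical 20-item physical score, the ratio was 0.91–4.26. It fell below 1 in 9 of 270 settings, all with ρ = 0.85, mood loading 0.3 and 3–4 physical PHQ-9 items. With mood items almost unrelated to mood (loading 0–0.1), the ratio against the 10-item subscore was 0.77–1.11.

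**The case against.** **The item content is not shown.** Dimension names and the word half do not establish that items are shared with PHQ-9 or GAD-7. This stands. The protocol should not be asked to declare shared items as fact; it can only say what its own description says, that the total includes depressive and anxiety dimensions.

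**SSD is openly defined as a four-dimension score.** Its association with mood scales then follows from the definition, and the plan never says SSD means physical complaints only. This also stands, and it is why the bands should stay. It does not remove the difficulty: an association that follows from the definition is not evidence that physical symptoms accompany mood disorder.

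**No stated objective rests on this regression.** The objectives are prevalence, differences between age groups, and SSD risk factors in the elderly; the risk-factor model does not name PHQ-9 or GAD-7. Correct, and this limits the reach of the point. Still, the regression is planned, and two of the three endpoints combine the scales. The second objective also names physical and psychological differences separately, so a physical subscore has a use there.

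**The simulation is not the planned analysis.** It is unadjusted, uses continuous scores instead of severity bands and, at item level, covers PHQ-9 only. The subscore odds ratio of 1.0 needs wholly unrelated traits. All true; the figures show direction and sensitivity only.

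**The remedy leaves ambiguity.** A gap between total and subscore mixes content, length and any overlap remaining in the subscore. This is right and must be said beside the result. It does not make the subscore estimate uninformative.

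**Conclusion.** The concern holds in a limited form, with moderate confidence, and should be fixed before analysis. By the plan's own description, PHQ-9 and GAD-7 disorders are related to a total that appears to be about half mood content, and nothing planned separates the two, so the association is partly built in. This rests on the inferred item split. The boundary cases also assume equal-range, unweighted items.

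The size is unknown. Under assumed inputs the total-score association usually exceeds the physical-item one, but part of that excess can be scale length. The order can reverse when the non-physical items track mood only weakly, or when PHQ-9 items reflect physical symptoms and the traits are highly correlated.

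A reader might infer more: that the whole association is an artefact, that the bias is always upward, or that the SSD prevalence and the endpoint 2 and 3 counts are wrong. The documents support none of these. A real link between physical symptoms and mood may exist as well. The direction depends on item properties the documents do not give. The counts and prevalences are correct for the definitions the plan states.

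**What to change.** Keep the total-score bands and endpoints 2 and 3 as defined. Add to the Statistical Analysis section:

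1. **A pre-specified sensitivity analysis.** Repeat the depression and anxiety regressions (disorder yes/no as the dependent variable, same covariates) with the physical-item subscore as predictor: once per SD, and once in ordered groups such as quartiles, labelled descriptive, to parallel the severity bands. Show the SSS-CN total per SD beside it, from a separate model.
2. **A table.** Give the median, quartiles and number at or near the lowest possible physical subscore, among SSD cases and among endpoint 2 and 3 cases. Label any threshold descriptive.
3. **A limitation statement.** The SSS-CN total includes depressive and anxiety dimensions by its own description, so its association with PHQ-9 and GAD-7 is not by itself evidence that physical symptoms accompany mood disorder. The gap between total and subscore is not a clean measure of bias, because of scale length and possible residual overlap.

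**Cost.** One extra model set and one table, with no new data. Exclusion criterion (4) removes "patients with any missing data within questionnaire items", so the subscore is complete for every analysed participant despite the general mention of multiple imputation.

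**Precision.** In the 270-setting simulation the standard error of the subscore log odds ratio at N = 9110 was 0.0228–0.0402. That gives exp(1.96 × SE) = 1.05–1.08, or about ±5% to 8%. For the 2236 non-elderly, multiplying by √(9110/2236) = 2.02 gives about ±9% to 17%. These figures are unadjusted and ignore clustering.

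**Downside.** The subscore has no stated cut-off, so it cannot replace SSD yes/no or redefine endpoints 2 and 3.

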	
(yes/no), endocrine and metabolic disease except DM (yes/no), other diseases (yes/no), surgery (yes/no) and antipsychotic intake (yes/no) in all models.
 
Univariate analyses and binary logistic regression models will be used to assess the effects of sociodemographic factors and clinical characteristics on SSD in the non- elderly and elderly. Categorical sociodemographic and clinical variables will be analyzed by chi-square test. Binary logistic regressions will be performed using SSD (yes/no) as the dependent variable, adjusting for gender, educational level, marital status, and antipsychotic intake.
 
Fisher's exact test was used instead of the chi-square test only when one or more expectations for each cell of the 2-by-2 tables was below 5. A significance level was set at a p-value < 0.05 (two-tailed). Missing data were imputed with a multiple imputation approach. All statistical analyses were performed with SPSS 22 (IBM SPSS Statistics for Windows, Version 22.0. Armonk, NY: IBM Corp).

--	---

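### The age-group models have no term for place, so the elderly versus non-elderly odds ratio is unprotected if age mix and SSD level vary together across institutions

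*Combined protocol and SAP*

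**What the plan says.** The Study Design section of the synopsis treats place as a design variable. Shanghai's districts are "divided into low, medium, and high economic levels according to the per capita gross domestic product of each district in 2018". Then "Eleven districts will be selected proportionally and randomly and represented by 105 community health service institutions".

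The Statistical Analysis section sets out two families of logistic model.

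- **Age-group models** (SSD, depression and anxiety against age group): "binary logistic regressions will be performed, adjusting for gender, educational level", then marital status, hypertension, diabetes, cardiovascular disease, other endocrine and metabolic disease and other diseases, ending with "surgery (yes/no) and antipsychotic intake (yes/no) in all models".
- **Risk-factor models** (SSD yes/no, for the elderly and the non-elderly): a shorter list of gender, education, marital status and antipsychotic intake.

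Neither list includes institution, district or economic level, whether as covariate, stratum, cluster or random effect. The Number of Subjects section gives the age split only overall (6874 elderly, 2236 non-elderly). No quota, matching or weighting that would hold the age mix constant across institutions is described.

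**The concern.** A logistic model without a place term estimates the age effect partly from people at the same institution and partly from differences between institutions. If institutions with a larger elderly share also have a higher (or lower) SSD level for reasons unrelated to age, that difference enters the age odds ratio. Such reasons could include local economic conditions or how the questionnaires are administered.

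The elderly versus non-elderly difference is the second primary objective. Confounding of this kind shifts the estimate itself, so cluster-robust or wider intervals would not remove it. With over 9000 participants, even a modest shift can reach p < 0.05.

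**Working it through.** **Inputs from the synopsis.** 6874 + 2236 = 9110, which matches the stated enrolment. The elderly share is 6874/9110 = 75.5%. Per institution, on average: 9110/105 = 86.8 people, of whom 6874/105 = 65.5 are elderly and 2236/105 = 21.3 are not. The plan states no power calculation or effect size to reproduce.

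**Assumed, because the documents do not give them.** SSD prevalence, the variation of SSD and of elderly share between places, and the correlation between the two. All illustrations below are unadjusted; the planned covariates are left out.

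**Step 1: when the problem arises.** Let place k have elderly share s_k and SSD prevalence p_k, the same for both age groups (true odds ratio 1.00). With equal-sized places and mean share s̄,

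pE = Σ s_k p_k / Σ s_k, pN = Σ (1 − s_k) p_k / Σ (1 − s_k), and pE − pN = Cov(s, p) / [s̄(1 − s̄)].

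At the null there is no distortion if the covariance is zero, for example if every place has the same elderly share.

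**Step 2: three economic levels.** Take mean SSD 40%, with elderly share and SSD both moving ±10 points across the levels. Cov = 0.1 × 0.1 × 2/3 = 0.00667 and s̄(1 − s̄) = 0.7546 × 0.2454 = 0.1852, so pE − pN = 0.0360. Directly, pE = 0.4088 and pN = 0.3728, and the odds ratio is (0.4088/0.5912)/(0.3728/0.6272) = 1.16.

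SE of the log odds ratio = √[1/(6874 × 0.4088 × 0.5912) + 1/(2236 × 0.3728 × 0.6272)] = 0.050. Then ln 1.163/0.050 ≈ 3.0, so a nominal 5% test rejects about 86% of the time.

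Swings of ±5/±5 give an odds ratio of 1.04 (about 12% rejection), and ±15/±15 give 1.41. The direction reverses if the two move in opposite directions.

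**Step 3: 105 institutions.** Simulation with 105 sites of 87 people, 75% elderly, true odds ratio 1.00, SD 0.3-0.5 for site SSD log-odds and 0.5-1.0 for the logit of site elderly share. The crude odds ratio is compared with the Mantel-Haenszel odds ratio stratified by institution.

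| Correlation between sites | OR ignoring place | OR stratified by institution |
|---|---|---|
| 0 | 1.00 | 1.00 |
| 0.1 | 1.01-1.05 | 0.99-1.01 |
| 0.3 | 1.04-1.14 | 0.99-1.01 |
| +0.5 | 1.07-1.23 | 0.99-1.01 |
| −0.5 | 0.82-0.94 | 0.99-1.01 |

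For correlations of 0.3 or more in size, the test ignoring place rejects in about 7-77% of runs at 10% SSD prevalence and 17-95% at 40%. Repeat runs move these ends by a few points. The stratified test rejects in about 3-7%. The spread of the log odds ratio is nearly the same for the two estimates: about 0.05-0.06 for both at 40% prevalence and 0.08-0.09 at 10%.

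At zero correlation neither estimate is biased. The test ignoring place still rejects somewhat too often, up to about 14% in these settings, because chance imbalance across 105 sites is not counted in its standard error.

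**The case against.** The strongest objection is that the bias is hypothetical. The synopsis gives no elderly share or SSD level by institution, district or economic level. A reader might infer from the missing term that the age odds ratio is biased. The documents do not support that: they show only that the plan does not guard against it. This objection stands and sets the limit of the point.

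The illustrations also do not test the planned model. Education and the disease covariates may carry part of any difference between economic levels, so the figures probably lean towards the upper end for the assumed inputs. Rejection rates depend strongly on prevalence, which is not given for SSD, depression or anxiety; no single range serves all three outcomes. In the mildest settings the odds ratio moves by only 1-5%. All of this stands. But personal characteristics do not substitute for a place term.

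Two premises rest on silence in a short synopsis. It does not describe how people are selected within institutions, so an unstated age quota cannot be excluded. Nor does it say that institution is recorded for each participant, although recruitment through institutions makes that likely.

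Finally, the second primary objective can be read as a population comparison, and a within-institution odds ratio answers a somewhat different question. Away from the null the two also differ through non-collapsibility, without any confounding. That gap is small here: with a within-level odds ratio of 1.50, equal elderly shares and SSD swings of ±10 points, the pooled odds ratio is 1.48. Reporting both estimates meets this objection.

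**Conclusion.** The point holds in conditional form. The design samples by economic level through 105 institutions, the age-group models contain no place term, and no stated feature fixes the age mix by site. The elderly versus non-elderly odds ratio is therefore open to confounding by place.

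Its size and direction cannot be read from the documents. Under the assumptions above, the distortion ranges from none at zero correlation, through a few per cent at weak correlation, to about 20% in either direction at correlations of ±0.5. The rejection rates illustrate what could happen and do not predict this study's error rate. Comparing within institution removes the distortion in every scenario tried, with almost no loss of precision, so it is a worthwhile and inexpensive improvement.

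**What to change.** - In the age-group models of SSD, depression and anxiety, condition on institution, by conditional logistic regression or institution fixed effects. State that the odds ratio is a within-institution comparison.
- Report the planned model without place alongside it, so that the reader can see how much place matters.
- Add district economic level (low, medium, high) as a covariate in the risk-factor models for the third objective.

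The cost is analysis wording, with no new data provided institution is recorded for each participant. Institutions with only one age group, or with no variation in the outcome, add nothing to the within-institution estimate; at about 65 elderly and 21 non-elderly per site on average, few should be lost unless enrolment is very uneven or the outcome is rare. The conditional odds ratio can also differ slightly from the pooled one through non-collapsibility, and the text should say so.

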Prevalence and characteristics of somatic symptom disorder in the elderly in a community-based population: a large-scale cross-sectional study in China

Assessment of Somatic Symptom in Chinese Community-Dwelling People

Protocol Number	SSSCN202011
NCT No.	NCT04815863
Date	Sep 20, 2018

STUDY PROTOCOL SYNOPSIS

Title	Prevalence and characteristics of somatic symptom disorder in the elderly in a community-based population: a large-scale cross-sectional study in China
Sponsor	Investigator-Initiated Trial (IIT)
Primary Objectives	
 1. to clarify the prevalence of somatic symptom disorder (SSD), depressive disorders, and anxiety disorders in the elderly in China; 2. to identify physical and psychological differences between the elderly and non-elderly; 3. to explore risk factors for SSD in the elderly.

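### SSD risk factors are assessed in the elderly and the non-elderly without any comparison of effects between them, so a difference in significance could be misread as a difference by age

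*Combined protocol and SAP*

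**What the plan says.** All references are to the synopsis tables of the combined protocol and SAP.

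- **Primary Objectives.** Objective 2 is "to identify physical and psychological differences between the elderly and non-elderly". Objective 3 concerns risk factors for SSD and names the elderly only.
- **Number of Subjects.** 9110 participants are anticipated: 6874 elderly and 2236 non-elderly.
- **Statistical Analysis, risk factors.** Univariate tests and logistic models are to "assess the effects of sociodemographic factors and clinical characteristics on SSD in the non- elderly and elderly". The model is described as follows: "Binary logistic regressions will be performed using SSD (yes/no) as the dependent variable, adjusting for gender, educational level, marital status, and antipsychotic intake". Age group is not listed and there is no product term.
- **Statistical Analysis, age group.** A different set of regressions asks "whether SSD, depressive and anxiety disorders are associated with aged groups". It adjusts for ten covariates and estimates the main effect of age group.
- **Statistical Analysis, significance.** "A significance level was set at a p-value < 0.05 (two-tailed"), stated once for all analyses.

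The text does not use the word separately for the risk-factor models. One model per age group is inferred from the wording and from the covariate list.

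**The concern.** Objective 3 can be met by the elderly model alone. Running the same analysis in the non-elderly puts a second set of results beside it, in a study whose second objective is to find differences between the groups. The plan gives no means of judging whether two odds ratios for the same factor differ. The age-group regressions do not help: they ask whether SSD is more common in one group, not whether, say, marital status is more strongly related to SSD in one group.

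A reader, or the authors, may then compare which factors reach p < 0.05 in each group. A factor with an identical effect in both can pass the threshold in the larger group and miss it in the smaller one, and be described as a risk factor for the elderly only. Prevalence estimates are unaffected. Statements about risk factors that set elderly against non-elderly are what is at stake.

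**Working it through.** **Inputs from the documents.** n(elderly) = 6874, n(non-elderly) = 2236, two-sided alpha = 0.05. The sizes add up to the stated total: 6874 + 2236 = 9110. Their ratio is 6874/2236 = 3.07. No power, effect size, SSD prevalence or exposure prevalence is given, so no planned power can be reproduced.

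**Assumptions.** The same true odds ratio, SSD prevalence and factor distribution in both groups; no covariate adjustment; no clustering.

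**Step 1: standard errors.** SE(non-elderly)/SE(elderly) = sqrt(6874/2236) = 1.753.

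**Step 2: power in the smaller group.** If power in the elderly is P, the expected z-value there is 1.96 + Phi^-1(P). In the non-elderly it is that value divided by 1.753, and power is Q = 1 - Phi(1.96 - z/1.753). For P = 0.80: z = 1.96 + 0.842 = 2.802; 2.802/1.753 = 1.598; Q = 1 - Phi(0.362) = 0.36.

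**Step 3: discordance.** Significant in the elderly only: P(1 - Q). Significant in the non-elderly only: Q(1 - P). The last column repeats the calculation for the same effect with 4555 per group, where z is divided by sqrt(6874/4555) = 1.228.

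| Elderly power | Non-elderly power | Elderly only | Non-elderly only | Total discordance | Total with equal groups |
|---|---|---|---|---|---|
| 60% | 24% | 45% | 10% | 55% | 49% |
| 80% | 36% | 51% | 7% | 58% | 47% |
| 90% | 46% | 49% | 5% | 54% | 37% |
| 95% | 54% | 44% | 3% | 47% | 28% |
| 99% | 69% | 31% | 0.7% | 32% | 12% |
| 99.9% | 82% | 18% | 0.1% | 18% | 3% |

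With equal groups the total divides evenly between the two directions.

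**Step 4: in terms of odds ratios.** Two-proportion power was calculated over an assumed grid (SSD prevalence 10-50%, exposure 10-40%, odds ratio 1.2-1.5) and checked with 200,000 simulated pairs of tables per scenario.

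- At 20% SSD and 20% exposed, an odds ratio of 1.2 gives power of 70% and 30%, with elderly only 49% and non-elderly only 9%. An odds ratio of 1.5 gives 100% and 89%, with elderly only 11%.
- Over the grid, elderly only is 14-51% for odds ratios of 1.2-1.3 and 0.3-45% for 1.5. The lowest value is at 50% SSD and 40% exposed. Non-elderly only never exceeds 11%.

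**Step 5: a direct comparison.** A Wald test of the difference in log odds ratios was falsely positive in 4.8-5.1% of simulations with identical true odds ratios. For 80% power it needs a ratio of odds ratios of about 1.3 to 2.05 across the grid, and about 1.5 at 20% SSD and 20% exposed.

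**The case against.** The strongest reply is that the misreading is predicted, not planned. A reader might infer that the protocol intends to label factors as elderly-specific from their p-values. The documents do not support that: no sentence says so, objective 3 is exploratory and confined to the elderly, and objective 2 speaks of physical and psychological differences, not of differences in risk-factor effects. Parallel description is a possible reason for the non-elderly model. This stands, and it makes the point conditional on the two sets of results being compared.

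Three further limits also stand.

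- It would be wrong to say that the plan yields only p-values. Logistic models give odds ratios in each group, and the significance level is a general statement, not a stated rule for selecting factors.
- Blaming the threefold size difference alone is too strong. At 80% elderly power, discordance is 58% with the planned split and 47% with equal groups. The imbalance mainly tilts discordance towards the elderly; at higher power it also adds to it.
- Equal prevalence and factor distribution across ages is doubtful for items such as widowhood or hypertension, and the problem fades for strong, common factors.

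What the reply does not remove is the gap itself. If factor effects are compared between the age groups, the plan supplies no valid way to do so.

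**Conclusion.** The point holds in conditional form. The plan assesses SSD risk factors in both age groups, by natural reading one model each, and contains no comparison of effects between them; its age-group regressions test a main effect only. Differences in significance between the two models cannot show that a factor is particular to the elderly. With identical true effects, the chance of significance in the elderly only is 45%, 51%, 49%, 44%, 31% and 18% at elderly power of 60%, 80%, 90%, 95%, 99% and 99.9%. These figures rest on equal odds ratios, SSD prevalence and factor distribution, none of which the documents give, and they ignore adjustment and clustering. The change is worth making as a cheap improvement. It does not correct a declared error, and neither the prevalence results nor the elderly model taken by itself is put in doubt.

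**What to change.** - Keep the stratified models and report odds ratios with 95% confidence intervals in both groups.
- Add one pooled logistic model with age group, the sociodemographic and clinical factors assessed in the risk-factor analysis, and age-group-by-factor terms. Name the factors explicitly, because the Statistical Analysis section has a ten-term and a four-term covariate list. Use one joint test for each multi-level factor (education, marital status) and merge sparse categories.
- Report the ratio of odds ratios, elderly to non-elderly, with its 95% confidence interval, labelled exploratory.
- State that a factor will be described as specific to, or stronger in, the elderly only on the basis of that interaction, and not on which group reaches p < 0.05.

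The cost is one extra model, in the software already named, on data already to be collected. The downside is imprecision. With 2236 non-elderly, modest interactions will often be missed, so a non-significant interaction must not be read as equal effects, and fewer age-specific claims can be made.
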